### 10.3 Exploratory Objectives

There are six exploratory objectives for this study.

- a) The first exploratory objective (EO 1) is to compare time to first antibiotic, by EHR-based decision support or usual care.

The Wilcoxon rank-sum test will be used to compare time to first antibiotic between intervention and control arms.

A frailty regression model will be conducted. The outcome is time to first antibiotic and participants not receiving antibiotics shall be censored at discharge. The covariates under the consideration will be similar to the ones listed in the primary objective analysis 10.1.

- b) The second exploratory objective (EO 2) is to compare the proportion of participants not receiving antibiotics during the first 24 hours of care, by EHR-based decision support or usual care.

Proportions of participants not receiving antibiotics during the first 24 hours of care (yes or no) will be compared between intervention and control arms using a Chi-square test. Proportions and difference of proportions between intervention and control arms will be reported along with their 95% CIs.

A mixed effects logistic regression model will be conducted. The outcome is lacking of antibiotics during the first 24 hours of care (yes or no) and covariates under the consideration will be similar to the ones listed in the primary objective analysis 10.1.

- c) The third exploratory objective (EO 3) is to compare the proportion of participants not receiving antibiotics for the entire episode, by EHR-based decision support or usual care.

The analysis is similar to exploratory objective 2 though the proportion of lacking of antibiotics for the entire episode is the outcome.

- d) The fourth exploratory objective (EO 4) is to compare the changes in antibiotics, used as a proxy for treatment failure, after 72 hours, by EHR-based decision support or usual care.

The analysis is similar to exploratory objective 2 though the proportion of participants with different antibiotic(s) or changing treatments from no-antibiotic(s) to antibiotic(s) after 72 hours is the outcome.

- e) The fifth exploratory objective (EO 5) is to compare the proportion of death, by EHR-based decision support or usual care.

The analysis is similar to exploratory objective 2 though the proportion of death is the outcome.

- f) The sixth exploratory objective (EO 6) is to compare the proportion of delayed ICU transfer among hospitalized children, by EHR-based decision support or usual care.

The analysis is similar to exploratory objective 2 though the proportion of delayed ICU transfer among hospitalized children is the outcome.

## **11 ANALYSIS OF STUDY OBJECTIVES FOR PHASE 2**

Descriptive analyses will be summarized for continuous variables with mean, standard deviation, median, and interquartile range. Categorical variables will be summarized with frequencies and percentages. Explanatory figures will be generated to evaluate the data distribution. Comparisons of demographic characteristics between intervention groups will be conducted using Pearson Chi-square and Wilcoxon tests appropriately.

All analyses will be performed using R 3.5.0 (r-project.org), SAS version 9.4, or STATA version 15, or updated software from these programs.

### **11.1 Primary Objective**

The primary objective (PO 1) of the study is to compare proportions of appropriate overall site of care disposition with or without EHR-based prognostic decision support in children 0.6-17 years of age presenting for emergency care. The hypothesis for this primary objective is that the proportion of appropriate site of care disposition is higher in the group receiving EHR-based prognostic decision support vs. the group receiving usual care. This information is captured through chart review and entered in the REDCap database. An investigator in both Nashville and Pittsburgh will be in charge of outcome assessment review, blinded to intervention assignment, and will decide whether site of care disposition is appropriate, yes (1) or no (0), based on Appendix 2 table for this analysis.

The proportions will be compared between the intervention arm versus the control arm using a Cochran-Mantel-Haenszel method in a stratified analysis by site to control for two sites at the alpha 0.05 level. The proportion difference and corresponding 95% confidence interval for concordance of antibiotics with or without adjusting for sites will also be calculated.

We will conduct a multivariable logistic regression model to compare appropriate site of care disposition between the two study arms, controlling for important baseline covariates. Important baseline covariates (e.g., age, sex, race, site, season, month, frequency of bacteremia and other pneumonia-related complications) will also be assessed and included as model covariates. Robust standard errors will be calculated to account for hospital clustering effects. We will also perform analyses to assess for interactions between two study arms and predicted risk for severe outcomes, age, provider type, and initial site of care, to identify subgroups in whom decision support may be most useful.

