clinical setting. This process resulted in a pool of 20 predictors. We also created a separate, more parsimonious model restricted to 9 predictors commonly available within electronic health records (EHR).

Both models accurately identified risk for moderate or severe pneumonia, indicating strong potential to improve risk stratification. Model discrimination, which measures the degree of concordance between observed and predicted outcomes, was excellent with a c-index ranging from 0.78-0.81. Differences in model fit and quality were considered negligible, and results from the internal bootstrap validation were comparable to the primary models. In the full model, PaO₂:FiO₂ ratio (PF ratio, estimated from the SaO₂:FiO₂ ratio),²⁴ age, heart and respiratory rates, altered mental status, temperature, chest indrawing, infiltrate pattern, and systolic blood pressure were the strongest predictors, contributing 96% of the explainable outcome variation. The EHR model retained most of these predictors (omitting altered mental status, chest indrawing, and infiltrate pattern). Nonetheless, predictive performance of the EHR model equaled that of the full model. For the full model, the median predicted risk for moderate or severe pneumonia was 18% (IQR 9-32%) and for severe pneumonia 5% (3-11%).

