8.4 Power and Sample Size (P2)

As outlined in P1, we anticipate nearly 2000 children with pneumonia will be evaluated annually during the conduct of these studies. Assuming conservatively that data for 2000 children (1000 in each arm) are captured during the two-year study period, and 90% appropriate site of care disposition in the usual care arm (based on data from the EPIC cohort)²³, we will be able to detect an absolute difference of $\geq 3.4\%$ in appropriate care disposition at an alpha level of 0.05 with 80% power.

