8.5 Analysis (P2)

Logistic regression models will be performed to compare appropriate site of care disposition between the two study arms, controlling for important baseline covariates (e.g., age, season, provider type) to maximize power. Robust standard errors will be calculated to account for hospital clustering effects. We will also perform analyses to assess for interactions between two study arms and predicted risk for severe outcomes, age, provider type, and initial site of care, to identify subgroups in whom decision support may be most useful. Similar analyses will be conducted for the proposed secondary and exploratory outcomes along with cox regression model for hospital length of stay outcome.

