### **6.2.2 Phase 2**

As outlined in P1, we anticipate nearly 2000 children with pneumonia will be evaluated annually during the conduct of these studies. Assuming conservatively that data for 2000 children (1000 in each arm) are captured during the two-year study period, and 90% appropriate site of care disposition in the usual care arm (based on data from the EPIC cohort), we will be able to detect an absolute difference of  $\geq 3.4\%$  in appropriate care disposition at an alpha level of 0.05 with 80% power.

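### The Phase 2 adjusted model does not pre-specify predicted risk at presentation as a covariate, although the planned interaction analysis already needs that value in both arms

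*SAP*

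**What the plan says.** SAP 11.1 plans two analyses of the Phase 2 primary outcome. The first compares the arms "using a Cochran-Mantel-Haenszel method in a stratified analysis by site to control for two sites at the alpha 0.05 level". The second is a multivariable logistic model with robust standard errors for hospital clustering. Its covariates are introduced as "Important baseline covariates (e.g., age, sex, race, site, season, month, frequency of bacteremia and other pneumonia-related complications". SAP 11.2 and 11.3 carry this list over to the models for the secondary and exploratory outcomes.

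Protocol 8.5 presents logistic regression as the comparison itself, "controlling for important baseline covariates (e.g., age, season, provider type) to maximize power". It does not mention a CMH test.

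Predicted risk appears in SAP 11.1 and Protocol 8.5 only as one of the factors to be tested for interaction with arm. Protocol 7.4 describes its automatic calculation for children in the decision support arm. Neither document says in terms that it will be calculated for controls.

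**The concern.** If covariates are chosen for power, the first candidate is a pre-treatment value that carries prognostic information and costs nothing to collect. The tool's predicted risk is built from variables available at presentation. Protocol 3.0 reports a c-index of 0.78-0.81 for disease severity and a wide spread of scores: "the median predicted risk for moderate or severe pneumonia was 18% (IQR 9-32" (percent). The interaction analysis cannot be run without the score in both arms.

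The named covariates are demographic, calendar, site and provider variables, plus bacteremia and complications. Those last two are the nearest to severity, but they may become known only after the disposition decision.

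Two things are at stake in the adjusted comparison: some precision, and protection against chance differences in severity between the arms. The same omission passes to every model that copies the list.

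**Working it through.** **Inputs.** SAP 6.2.2: "Assuming conservatively that data for 2000 children (1000 in each arm) are captured during the two-year study period"; "90% appropriate site of care disposition in the usual care arm"; a detectable difference of 3.4 points "in appropriate care disposition at an alpha level of 0.05 with 80% power". Sidedness is not stated, so two-sided is assumed. No dropout is stated and none is applied.

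**Step 1: the plan's own figure.** With p0 = 0.90, p1 = 0.934, mean 0.917 and n = 1,000 per arm:

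- SE under the null = √(2 × 0.917 × 0.083 / 1000) = 0.01234
- SE under the alternative = √((0.90 × 0.10 + 0.934 × 0.066) / 1000) = 0.01231
- Power = Φ((0.034 − 1.96 × 0.01234) / 0.01231) = Φ(0.797) = 78.7%

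This reproduces the stated 80% within rounding. Exactly 80% needs 1,033 per arm, or a difference of 3.45 points. The figure is for an unadjusted comparison of two proportions, so it approximates the CMH test and owes nothing to covariates.

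**Step 2: analytic gain.** If the score explains a share R² of the outcome variance, the effective n per arm is 1000/(1 − R²). The documents give no R², so these values are assumptions.

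| R² | Effective n per arm | Power |
|---|---|---|
| 0 | 1,000 | 78.7% |
| 0.02 | 1,020 | 79.5% |
| 0.05 | 1,053 | 80.8% |
| 0.10 | 1,111 | 82.8% |
| 0.15 | 1,176 | 84.9% |

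Reaching 80% needs R² of about 1 − 1000/1033 = 0.03.

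**Step 3: simulated gain.** The simulation used 1,000 per arm, marginal rates of 90% and 93.4%, and one standard-normal covariate with a monotone relation to the outcome. It compared an unadjusted test with a logistic Wald test using model-based standard errors. There were 10,000 replicates per row, and 4,000 in the rows marked *. AUC is the assumed discrimination of the score for appropriate disposition.

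| AUC | Unadjusted | Adjusted | Gain (points) |
|---|---|---|---|
| 0.58* | 79.9% | 80.1% | 0.1 |
| 0.64 | 79.4% | 79.9% | 0.6 |
| 0.71 | 79.1% | 81.3% | 2.2 |
| 0.75 | 78.9% | 82.5% | 3.6 |
| 0.79 | 79.3% | 83.3% | 4.0 |
| 0.80* | 78.6% | 84.6% | 6.0 |

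Gains are taken before rounding. Each power has a simulation standard error of about 0.4 points (0.6 in the * rows), so the step between the last two rows is partly noise.

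**Step 4: a relation that is not monotone.** Suppose mid-range risk is least often appropriate. At AUC 0.61, unadjusted power is 78.8%, a linear term gives 78.7% and an added quadratic term 79.3%. At AUC 0.65 the figures are 78.7%, 78.6% and 79.8%. A linear term then gains nothing, and a curved one gains about 0.5 to 1 point.

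**Step 5: chance imbalance.** If allocation acts as random, the difference between arms in the mean standardised score has a standard deviation of √(2/1000) = 0.045. A difference beyond 1.96 × 0.045 = 0.09 standard deviations would arise in about 1 trial in 20. That is modest, but adjustment removes its effect on the comparison.

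**The case against.** The strongest objection is that the change does not touch the test that matters. The SAP attaches alpha 0.05 to the site-stratified CMH test, and the 78.7% belongs to that comparison. A reader might infer that the trial is giving up power in its primary test. Under the SAP it is not. That reading would need Protocol 8.5 to govern, with the logistic model as the primary comparison. This part of the objection stands in full, and it shows that the two documents need reconciling.

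Four further points stand in whole or in part.

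- **Not named is not excluded.** Both lists are examples, and an interaction model would normally carry the main effect of risk. But that is a separate subgroup analysis, and an open list commits nobody to the covariate or to its form.
- **The c-index does not carry over.** A reader might take 0.78-0.81 to mean that predicted risk is the best available predictor of this outcome. It measures discrimination for severity. Under Appendix 2, a low-risk child kept at home and a high-risk child with a long ICU stay can both be appropriate. The documents report no link between score and outcome, so the gain cannot be converted into a definite number of children saved.
- **The comparison model was empty.** The planned model already includes age, which Protocol 3.0 lists among the tool's strongest predictors, so the increment is probably smaller than shown.
- **The standard errors differ.** The plan uses robust errors for clustering by hospital, with only two hospitals. The simulated power does not describe that test exactly.

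Missing inputs are also a real cost. A complete-case model that lost a few percent of children could cancel a gain at the low end of the range.

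**Conclusion.** The concern holds as a gap in pre-specification. Protocol 8.5 adjusts for power, and the trial needs predicted risk in both arms for a planned analysis, yet neither document commits to it as a covariate in the adjusted comparison.

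The benefit is uncertain: roughly 0 to 6 power points over an unadjusted model for assumed AUCs of about 0.60 to 0.80, and close to nothing at the lower end. It is confined to the logistic model. It rests on an association that the documents do not report, on two-sided testing and on model-based standard errors. Removal of chance severity imbalance does not depend on which test is primary, but it too applies only to the adjusted result. The case for acting is that the cost is low, not that the gain is large.

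**What to change.** In SAP 11.1, and in the models of 11.2 and 11.3 that copy its covariates:

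1. Name predicted risk at presentation as a required main-effect covariate. Enter its logit as a restricted cubic spline, because the relation to appropriateness may not be monotone.
2. State that the score is computed by the same program, from EHR data recorded before disposition, in both arms, and is not displayed for controls. This also secures the interaction analysis. Protocol 4.2 describes a readmission trial at one of the institutions that works in this way.
3. Give a simple rule for missing score inputs, identical in both arms and blind to arm and outcome, so that no child drops out of the model.
4. State whether the site-stratified CMH test or the adjusted logistic model is the primary test, and bring Protocol 8.5 and SAP 11.1 into line.

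The cost is a few sentences in the SAP, background scoring of control children, and two or three model degrees of freedom. No new data collection is needed.

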### **7.2 Analytic Issues**

There are two sites participating in the study and analysis of the primary objective will be stratified by site to account for site variation. There will be one primary objective per aim evaluated at the alpha 0.05 level. There will be no adjustments to the alpha level for all secondary and exploratory analyses.

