### **11.2 Secondary Objectives**

There are three secondary objectives for this study.

- a) The first secondary objective (SO 1) is to compare proportions of appropriate site of care disposition, by EHR-based prognostic decision support or usual care.

The analysis is similar to primary objective 1 though proportions of appropriate site of care disposition is the outcome.

- b) The second secondary objective (SO 2) is to compare proportions of participants having ED revisits and hospitalizations within 72 hours of the index discharge, by EHR-based prognostic decision support or usual care.

Proportions of participants having ED revisits or hospitalizations within 72 hours of the index discharge will be compared between intervention and control arms using Chi-square tests. Proportions and difference of proportions between intervention and control arms will be reported along with their 95% CIs.

Two multivariable logistic regression models clustering by hospitals will be conducted. The outcomes are ED revisits (yes or no) and hospitalizations (yes or no) within 72 hours of the index discharge and covariates under the consideration will be similar to the ones listed in the primary objective analysis 11.1.

- c) The third secondary objective (SO 3) is to compare proportions of participants having ED revisits and hospitalizations within 7 days of the index discharge, by EHR-based prognostic decision support or usual care.

The analysis is similar to secondary objective 2 though proportions of having ED revisits and hospitalizations within 7 days of the index discharge are the outcomes.

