### **11.3 Exploratory Objectives**

There are two exploratory objectives for this study.

- a) The first exploratory objective (EO 1) is to compare the proportion of death, by EHR-based prognostic decision support or usual care.

The analysis is similar to secondary objective 2 though the proportion of death is the outcome.

- b) The second exploratory objective (EO 2) is to compare hospital length of stay among hospitalized children, by EHR-based prognostic decision support or usual care.

The Wilcoxon rank-sum test will be used to compare length of stay between intervention and control arms.

A cox regression model will be conducted. The outcome is length of stay. The covariates under the consideration will be similar to the ones listed in the primary objective analysis 11.1.

## Appendix 1

Prior B-lactam	Severe PCN allergy	Moderate to large PPE	Necrotizing or severe pneumonia	Aspiration	Outpatient	Inpatient	ICU without invasive mechanical ventilation or shock	ICU WITH invasive mechanical ventilation and without shock	ICU WITH invasive mechanical ventilation AND shock
NO	NO	NO	NO	NO	Amoxicillin	Ampicillin	Ampicillin or Ceftriaxone	Ceftriaxone	Ceftriaxone plus Vancomycin
NO	NO	NO	NO	YES	Amoxicillin/Clavulanate	Ampicillin/Sulbactam	Ampicillin/Sulbactam or Clindamycin	Ampicillin/Sulbactam or Clindamycin	Ceftriaxone plus Vancomycin
NO	NO	NO	YES	NO	n/a	Ceftriaxone plus Clindamycin or Vancomycin	Ceftriaxone plus Clindamycin or Vancomycin	Ceftriaxone plus Vancomycin	Ceftriaxone plus Vancomycin
NO	NO	NO	YES	YES	n/a	Ceftriaxone plus Clindamycin or Vancomycin	Ceftriaxone plus Clindamycin or Vancomycin	Ceftriaxone plus Vancomycin	Ceftriaxone plus Vancomycin
NO	NO	YES	NO	NO	n/a	Ampicillin	Ceftriaxone plus Clindamycin or Vancomycin	Ceftriaxone plus Clindamycin or Vancomycin	Ceftriaxone plus Vancomycin
NO	NO	YES	NO	YES	n/a	Ampicillin/Sulbactam	Ceftriaxone plus Clindamycin or Vancomycin	Ceftriaxone plus Clindamycin or Vancomycin	Ceftriaxone plus Vancomycin
NO	NO	YES	YES	NO	n/a	Ceftriaxone plus Clindamycin or Vancomycin	Ceftriaxone plus Clindamycin or Vancomycin	Ceftriaxone plus Vancomycin	Ceftriaxone plus Vancomycin
NO	NO	YES	YES	YES	n/a	Ceftriaxone plus Clindamycin or Vancomycin	Ceftriaxone plus Clindamycin or Vancomycin	Ceftriaxone plus Vancomycin	Ceftriaxone plus Vancomycin

NO	YES	NO	NO	NO	Clindamycin	Clindamycin	Clindamycin or Levofloxacin	Levofloxacin	Levofloxacin plus Vancomycin

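### The Phase 2 adjusted logistic models cluster their standard errors on only two hospitals, so their confidence intervals and p-values are unreliable; the site-stratified CMH test is not affected

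*SAP*

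**What the plan says.** SAP 7.2: "There are two sites participating in the study and analysis of the primary objective will be stratified by site to account for site variation". It adds: "There will be one primary objective per aim evaluated at the alpha 0.05 level". Protocol 4.2 and SAP 6.3.2 allocate Phase 2 at the level of the patient.

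SAP 11.1 (Phase 2) gives two comparisons of the primary outcome. The first is made "using a Cochran-Mantel-Haenszel method in a stratified analysis by site to control for two sites at the alpha 0.05 level". The second is a multivariable logistic regression, for which "Robust standard errors will be calculated to account for hospital clustering effects". Its covariate list includes site: "Important baseline covariates (e.g., age, sex, race, site, season, month, frequency of bacteremia and other pneumonia-related complications".

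Protocol 8.5 names only the logistic regression, "controlling for important baseline covariates (e.g., age, season, provider type) to maximize power", with the identical sentence on robust standard errors. It does not mention the CMH test.

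For the secondary outcomes SAP 11.2 states: "Two multivariable logistic regression models clustering by hospitals will be conducted". For death, SAP 11.3 states: "The analysis is similar to secondary objective 2 though the proportion of death is the outcome".

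Neither document gives a reference distribution, degrees of freedom or a small-sample correction for the clustered standard errors. SAP 11 leaves the software open among three packages, so the choice would fall to package defaults.

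**The concern.** A cluster-robust variance learns about sampling error from the spread between clusters, so it needs many of them. With two hospitals there is one contrast. At the fitted estimate the hospital score totals sum to zero, so the second total is minus the first and the clustered variance matrix has rank 1. The standard error of the arm effect then reflects how closely two hospital estimates happen to agree. If they agree by chance, the interval is far too narrow.

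At stake are the standard errors, confidence intervals and p-values of the adjusted odds ratios and the interaction tests. On the same data they can contradict a valid CMH result.

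**Working it through.** **Inputs from the documents.** Two hospitals (SAP 7.2); individual 1:1 allocation (SAP 6.3.2); 1000 per arm, 90% in control, 3.4-point difference, alpha 0.05, 80% power (Protocol 8.4, SAP 6.2.2).

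**Assumed.** Two-sided test; site split (not given) 50:50 to 70:30, with 80:20 as an extreme; correction and reference distribution, each tried both ways.

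**Step 1: the plan's own power.** Pooled rate (0.90 + 0.934)/2 = 0.917.
- Null SE = sqrt(2 × 0.917 × 0.083/1000) = 0.01234.
- Alternative SE = sqrt((0.90 × 0.10 + 0.934 × 0.066)/1000) = 0.01231.
- z = (0.034 - 1.96 × 0.01234)/0.01231 = 0.797, so power is 78.7%.

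This agrees with the stated 80% to within 2 points; exactly 80% needs a 3.45-point difference.

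**Step 2: the clustered variance.** Let w be one hospital's share of the information, V the true variance of the arm estimate, and b1, b2 the hospital-specific estimates.
- Pooled estimate: b = w·b1 + (1-w)·b2.
- Clustered variance: 2·[w(1-w)]²·(b1-b2)².
- Var(b1-b2) = V/[w(1-w)], so the clustered variance is 2w(1-w)·V times a chi-square on 1 df. G/(G-1) = 2 doubles it.
- b and b1-b2 are uncorrelated, so the Wald ratio is a t(1) variable divided by s, with s = sqrt(2w(1-w)·c) and c = 2 (corrected) or 1 (uncorrected).

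**Step 3: size and power.** Size with critical value k is 1 - (2/π)·atan(k·s). For equal sites and k = 1.96:
- corrected, s = 1: 1 - (2/π)·atan(1.96) = 0.300
- uncorrected, s = 1/sqrt(2): 1 - (2/π)·atan(1.386) = 0.398

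For t(1), k = 12.706. Power uses noncentrality 1.96 + 0.84 = 2.80, the plan's 80% power.

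| Site split | Normal, corrected: size | Normal, uncorrected: size | t(1), corrected: size / power | t(1), uncorrected: size / power |
|---|---|---|---|---|
| 50:50 | 30.0% | 39.8% | 5.0% / 17.4% | 7.1% / 24.4% |
| 60:40 | 30.6% | 40.4% | 5.1% / 17.8% | 7.2% / 24.8% |
| 70:30 | 32.3% | 42.5% | 5.5% / 19.0% | 7.7% / 26.5% |
| 80:20 | 36.1% | 46.7% | 6.2% / 21.6% | 8.8% / 30.1% |

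**Step 4: simulated logistic fits.** 4000 trials per setting, n = 2000, splits 50:50 and 70:30; models with arm alone, arm and site, or arm, site, age, sex and season.
- Null, normal reference: 29.8-32.8% corrected, 39.0-43.4% uncorrected.
- t(1), corrected: size 4.8-5.5%, power 17.0-18.2%.
- Model-based standard errors with site in the model: size 4.6-5.3%, power 78-80%.
- CMH: size 4.6-5.4%, power 78-80%.

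A covariate set closer to the SAP list (site, age, sex, race, 12 months, complications; 2500 trials) gave 30-32% and 40-42%, against 5% for model-based standard errors.

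**Step 5: related output, under the null.** These runs used splits of 50:50, 60:40 and 70:30. The first two items used a model with arm, site, age, season and a two-level provider type, which is Protocol 8.5's example covariates plus site.
- Regression significant while CMH is not: 26-28% of trials corrected, 35-38% uncorrected.
- Arm-by-age interaction: 29.9-32.8% corrected, 39.5-43.5% uncorrected, 4.4-5.5% model-based.
- Assumed event rates of 3% and 8%, standing in for secondary outcomes: 29.9-33.2%, 39.7-43.7% and 4.0-5.6% respectively.

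Death was not modelled.

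**The case against.** **The decisive test is untouched.** This is the strongest reply, and it stands for the SAP. A reader might infer that the Phase 2 primary test carries a 30-40% false-positive rate. The documents do not support that. SAP 7.2 calls for a site-stratified primary analysis, and SAP 11.1 attaches alpha 0.05 to the CMH test alone. The secondary outcomes, and death by reference, also have unadjusted chi-square tests. What does not follow is that the regression is labelled supportive: no sentence says so, and Protocol 8.5 names nothing else.

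**Protocol 8.5 does not exclude site.** A reader might infer that its model omits site. Its covariates are given only as examples, so the list is silent on site. The remedy is to name site there, as SAP 11.1 does.

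**A t(1) reference would control the error.** This is true only with the G/(G-1) correction. Without it, size is about 7-8% at splits of 50:50 to 70:30. With it, power falls below 20% at those splits.

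**Hospitals do differ.** They do, but children in both arms are treated in each hospital. Site as a covariate or stratum therefore handles differences in level. If the aim were to allow for an arm effect that varies across hospitals in general, two hospitals could not estimate that variation.

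**Conclusion.** The concern holds for the standard errors, confidence intervals and p-values of the Phase 2 adjusted logistic models in Protocol 8.5 and SAP 11.1 to 11.3, including their interaction terms. With a normal reference, false positives are about 30-32% (corrected) or 40-43% (uncorrected). With t(1) and the correction, size is about 5% and power about 17-19%, against 78-80% for CMH or for model-based standard errors with site in the model. These figures rest on an assumed site split of 50:50 to 70:30 and an assumed correction and reference; a more uneven split is somewhat worse for size. The behaviour for death is unquantified.

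The odds-ratio point estimates and the CMH, chi-square and Wilcoxon tests are not affected. The primary inference is affected only if Protocol 8.5 is followed as written. This should be fixed, but it does not invalidate the Phase 2 design.

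**What to change.** 1. Delete hospital clustering from the Phase 2 logistic models in Protocol 8.5 and SAP 11.1 to 11.3.
2. Name site as a fixed covariate in both documents.
3. Specify model-based standard errors for the arm and interaction terms.
4. Align Protocol 8.5 with SAP 11.1 on which analysis is primary. CMH and an adjusted regression with model-based standard errors are both valid here; what matters is that one is named in both places.
5. Separately, correct a wording slip in SAP 11.1. The Phase 2 proportion difference and its interval are described for the Phase 1 antibiotic outcome; they should refer to appropriate site of care disposition.

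The cost is wording in two documents and one option in the code. No extra data are needed.
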